The primary safety endpoint of this study will be the first occurrence of hospitalization for major bleeding as defined in **Section III.A.5.** The primary safety analysis will be performed by the ITT principle based on randomized treatment assignment. Event-free survival rates will be compared using Cox proportional-hazards models, equivalent to the log-rank test. The test will be 2-tailed and will be performed at an overall alpha of 0.05.

III.F.5. Power

The original trial sample size of 20,000 participants was chosen to provide 85% power to detect a 15% RR reduction assuming a primary effectiveness endpoint rate of 5% per year in the higher risk arm. Uniform accrual of 24 months and a maximum follow-up of 30 months were assumed and so was a 5% annualized rate of loss to follow-up.

The time required to bring enrollment into a steady-state uniform accrual proved to be longer by 14 months, leading to a currently estimated 38-month anticipated total accrual period. Furthermore, maximum follow-up will be increased to a maximum of 50 months. Finally, the original sample size calculations conservatively assumed a 5% event rate in the higher risk arm, leading to an overall event

rate below 5%. Thus, it was necessary to update the original power calculations with these new assumptions, incorporating actual accrual patterns observed to date and extrapolating the steady state enrollment numbers observed currently.

With more available data at the time of the DSMB meeting in November 2019, we considered primary effectiveness endpoint rates of 4.6%, 4.8%, 5.0% and 5.2% per year in the higher risk arm, the annualized rate of loss to follow-up of 5%, 2-sided significance level alpha of 0.05, total enrollment duration of 38 months, and an extended maximum follow-up period of 50 months. We considered clinically meaningful RR reduction for the treatment effect between aspirin doses for primary effectiveness endpoint of 20%, 17.5%, and 15%. With these data, taking into account enrollment feasibility and the expected event rate and the necessary meaningful risk reduction, we selected a target sample size of 15,000 participants to be enrolled and a maximum follow up duration of 50 months. Table 6 presents calculations performed for a sample size of 15,000 using PASS software. 97

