Assuming an annualized event rate of 4.6% in the higher risk arm and a 15% RR reduction (annualized event rate 3.8% in the lower risk arm) leads to 88% power and requires 1322 primary outcome events.

For the primary safety endpoint of hospitalization for major bleeding, power calculations were based on

Table 6					
Overall annualized event rate (%)	Relative Risk	Annualized event rate in low risk group (%)	Annualized event rate in high risk group (%)	Number of Events	Power
4.2	0.800	3.7	4.7	1321	0.99
4.2	0.825	3.8	4.6	1320	0.96
4.2	0.850	3.9	4.5	1322	0.88
4.4	0.800	3.9	4.9	1381	0.99
4.4	0.825	4.0	4.8	1381	0.97
4.4	0.850	4.1	4.8	1383	0.89
4.6	0.800	4.1	5.1	1441	0.99
4.6	0.825	4.2	5.0	1442	0.97
4.6	0.850	4.2	5.0	1439	0.90
4.8	0.800	4.3	5.3	1501	1.00
4.8	0.825	4.3	5.3	1502	0.98
4.8	0.850	4.4	5.2	1503	0.92

estimated primary event rates of 2%, 2.5%, and 3% per year (in the higher dose arm); annualized rate of loss to follow-up of 5%; 2-sided significance level alpha of 0.05; 7,500 participants in each treatment arm; total enrollment of 38 months; and a maximum follow-up period of 50 months. The power of the chosen testing strategy to detect a statistically significant difference in hospitalization for bleeding under these assumptions is shown in **Table 7**. Under all event rate scenarios, there will be power greater than 85% to detect an RR reduction of 25%, and for event rates of 2.5% or greater, power will be close to 80% to detect an RR reduction of 20%.

III.F.6. Secondary Endpoints

Secondary endpoints include the components of the primary endpoint, coronary revascularization procedures, quality of life, and functional status (Section III.A.5.a). Time-to-event outcomes will be analyzed using the same approach as the one used for the primary endpoint. Variables collected on numerical scales will be analyzed as continuous variables. Linear repeated measures mixed model will be employed to compare the 2 treatments on the changes from baseline.

Table 7			
Annualized event rate in higher-dose arm	Relative risk reduction	No. of events	Power
2%	25%	436	86%
	20%	449	66%
	15%	461	42%
2.5%	25%	544	92%
	20%	559	76%
	15%	575	50%
3%	25%	651	96%
	20%	669	83%
	15%	688	58%

III.F.7. Prior Treatment Effect

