Statistical Analysis Plan

Aspirin Dosing: A Patient-Centric Trial Assessing Benefits and Long-Term Effectiveness **"ADAPTABLE"**

Protocol History

Version 1.0	May 1, 2020
Version 1.1	December 7, 2020
Version 1.2	February 9, 2021

Prepared by

[name], MS Biostatistician III Duke Clinical Research Institute

[name] Director, Center for Predictive Medicine Duke Clinical Research Institute

[name] Professor of Biostatistics Duke Clinical Research Institute

1	Sy	nopsis	
2	Stu	udy Aims	
	2.1	.1 Aim 1	
	2.1	.2 Aim 2	
	2.1	.3 Aim 3	
3	Da	ta Sources	
4	Ra	ndomization and Drug Allocation	4
5	Stu	udy Endpoints	5
	5.1	Primary Endpoint	
	5.2	Secondary Endpoints	
	5.3	Primary Safety Endpoint	
6	lde	entification of Endpoints	5
7	Su	mmary of Statistical Methods	6
	7.1	Baseline Demographics and Medical History	6
	7.2	Populations for Analysis	7
	7.3	Primary Effectiveness Comparison	7
	7.4	Primary Safety Comparison	
	7.5	Censoring Rules	
	7.6	Power	
	7.7	Secondary Endpoints	9
	7.8	Prior Treatment Effect	
	7.9	Handling of Missing Data	
	7.9	.1 Outcome Dates	
	7.9	.2 Event-free Survival Outcomes	11
	7.9	.3 Longitudinal Outcome Data	11
	7.10	Planned Sensitivity Analyses	11
	7.11	Subgroup Analyses (Heterogeneity of Treatment Effect)	
8	Та	bles and Figures	
9	Re	ferences	

1 Synopsis

To identify the optimal dose of aspirin for secondary prevention in patients with atherosclerotic cardiovascular disease (ASCVD), we conducted a pragmatic clinical trial in which 15,000 patients who are at high risk for ischemic events were randomly assigned in a 1:1 ratio to receive an aspirin dose of 81 mg/day vs. 325 mg/day. Study participants were enrolled over 38 months. Maximum follow-up was 50 months (extended from originally specified 44 months). The primary endpoint is a composite of all-cause death, hospitalization for MI, or hospitalization for stroke. The primary safety endpoint is hospitalization for major bleeding with an associated blood product transfusion.

Additional details about the inclusion and exclusion criterion are contained in the study protocol. Many of the following details are also contained in the study protocol, with some differences in proposed statistical methodology.

2 Study Aims

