7.6 Power

Calculations were performed using PASS software. For the primary effectiveness endpoint, power calculations were based on an estimated primary event rate of 5.5% per year (in the higher risk arm), annualized rate of loss to follow-up of 5%, two-sided significance level α of 0.05, 7,500 patients in each treatment arm, enrollment of 38 months and a maximum follow-up period of 44 months. The power of the chosen testing strategy to detect a statistically significant

difference under these assumptions is 85% if the relative risk reduction is 15%, corresponding to a total of 1246 primary effectiveness events.

In November 2019, the DSMB approved extended follow-up in response to updated power calculations based on observed primary event rates. Assuming 7,500 patients in each treatment arm, annualized rate of loss to follow-up of 5%, two-sided significance level α of 0.05, enrollment of 38 months and maximum follow-up period extended to 50 months, the power to detect a relative risk reduction of 15% is 88% when the overall primary event rate is 4.5% in the higher risk arm, corresponding to a total of 1322 primary effectiveness events.

For the primary safety endpoint, power calculations were based on an estimated primary event rate of 2.5% per year (in the higher risk arm), annualized rate of loss to follow-up of 5%, two-sided significance level α of 0.05, 7,500 patients in each treatment arm, enrollment of 38 months and a maximum follow-up period of 44 months. The power of the chosen testing strategy to detect a statistically significant difference under these assumptions is 81% if the relative risk reduction is 20%, corresponding to a total of 642 primary safety events.

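### Protocol Table 7's bleeding event counts do not fit its stated 50-month follow-up, so neither document gives the safety power of the adopted design; the effectiveness rate pair and the scale of RR also need reconciling

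*Protocol*

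**What the plan says.** **Safety power.** Protocol III.F.5 assumes "7,500 participants in each treatment arm; total enrollment of 38 months; and a maximum follow-up period of 50 months", with 5% annual loss and two-sided alpha 0.05. At 2.5% per year in the higher-dose arm and a 20% reduction, Table 7 prints 559 events and 76% power. The summary sentence says that "for event rates of 2.5% or greater, power will be close to 80% to detect an RR reduction of 20"%. SAP 7.6 takes the same rate, reduction, arm size, enrollment and loss with a 44-month maximum, and reports that power "is 81% if the relative risk reduction is 20%, corresponding to a total of 642 primary safety events". SAP section 1 records the change of design: "Maximum follow-up was 50 months (extended from originally specified 44 months".

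**Effectiveness power.** At 44 months and a 5.5% rate, SAP 7.6 says that power "is 85% if the relative risk reduction is 15%, corresponding to a total of 1246 primary effectiveness events". At 50 months it gives 88% and 1322 events for a rate of 4.5% in the higher risk arm, which it also calls the overall rate. The protocol text has 4.6% in that arm: "annualized event rate 3.8% in the lower risk arm) leads to 88% power and requires 1322 primary outcome events". It also says "we considered primary effectiveness endpoint rates of 4.6%, 4.8%, 5.0% and 5.2% per year in the higher risk arm". Table 6 puts 1322 events and 0.88 on 4.5% vs 3.9% (RR 0.850). It puts 4.6% vs 3.8% on RR 0.825, with 1320 events and 0.96.

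**Accrual.** The protocol describes its updated calculations as "incorporating actual accrual patterns observed to date and extrapolating the steady state enrollment numbers observed currently". Neither document gives the accrual curve.

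**The concern.** With rate, effect, arm size, enrollment and loss held equal, longer follow-up cannot produce fewer events unless accrual differs, and neither document says that accrual differs between the two safety calculations. Tables 6 and 7 stand in one section under the same stated design but imply different exposure.

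Bleeding is the primary safety endpoint, and a null result will be read against the stated power. A reader who wants the chance of missing a 20% reduction in bleeding at 2.5% per year finds 24% in the protocol or 19% in the SAP. Neither belongs to the 50-month design. The rate pair and the unstated scale of RR matter for a related reason: that sentence gives the scenario offered for the November 2019 choice of 15,000 patients and 50 months, and it cannot be reproduced as written.

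**Working it through.** **Inputs.** 7,500 per arm, enrollment over 38 months, 5% annual loss, two-sided alpha 0.05, and the rates and counts in Protocol III.F.5 (Tables 6 and 7) and SAP 7.6. The accrual shape is an assumption. Three slow-start shapes were tried: a power law, a linear ramp to steady state, and a low rate for the first 14 months. Annual rates were read both as hazards and as annual probabilities.

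**1. Table 7's powers follow from its own counts.** Power = Φ(½√D·|ln HR| − 1.96). For 559 events and HR 0.80: ½ × 23.64 × 0.2231 − 1.96 = 0.68, so 75% (printed 76%). All nine cells agree within about one point. The counts are therefore the problem, not the power formula.

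**2. Implied exposure** = events / (15,000 × mean rate of the two arms).

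| Source | Stated maximum follow-up | Example | Years per patient |
|---|---|---|---|
| Table 6 | 50 months | 1322 / (15,000 × 0.042) | 2.09–2.10 |
| Table 7 | 50 months | 559 / (15,000 × 0.0225) | 1.65–1.66 |
| SAP effectiveness | 44 months | 1246 / (15,000 × 0.0509) | 1.63 |
| SAP safety | 44 months | 642 / (15,000 × 0.0225) | 1.90 |

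A lower event rate should raise exposure slightly. It cannot cut it by about a fifth.

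**3. Can any accrual rescue the 50-month label?** Expected events per arm = 7,500 × mean over entry times t of [h/(h+g)]·[1 − exp(−(h+g)(F − t))], where h is the event hazard, g the loss hazard and F the cut-off. For the 2.5%/20% case at 50 months:

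- Uniform accrual: 786–794 events. On the hazard reading the two arms give 435.5 + 350.8 = 786.3.
- Nobody enrolled in the first 14 months: 625–631.
- Accrual forced to give 559: mean entry at about month 29 and about 70% enrolled in the last 12 months. The same curve gives only 1,024–1,034 effectiveness events, against 1322 in Table 6.
- Loss needed to reach 559 instead: about 23–27% per year on accrual fitted to Table 6, against the stated 5%.

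**4. Does 44 months fit?** The three shapes were fitted only to the SAP's 1246 effectiveness events at 44 months, with rates as annual probabilities. At 44 months the ramp gives 436.2/448.6/460.9, 544.0/559.4/574.7 and 651.2/669.6/688.0. Table 7 prints 436/449/461, 544/559/575 and 651/669/688. The largest gap over the three shapes is 1.1 events. With rates as hazards it is up to 9 events. The SAP's 642 instead matches uniform accrual at 44 months (644–650), but uniform accrual gives 1,407–1,440 effectiveness events, not the 1246 in the same section.

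**5. Safety power at a true 50 months**, accrual fitted to Table 6 (range over shapes and rate readings):

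| Rate / reduction | Printed in Table 7 | At 50 months |
|---|---|---|
| 2% / 25% | 436, 86% | 561–568, 93% |
| 2% / 20% | 449, 66% | 577–584, 76–77% |
| 2.5% / 20% | 559, 76% | 719–726, 85% |
| 3% / 20% | 669, 83% | 859–866, 90–91% |

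For the third row: ½ × √722 × 0.2231 − 1.96 = 1.04, so 85%. Accrual fitted to the SAP's 1246 instead gives 707–713 events and 84–85%.

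**6. Rate pair.** 3.8/4.6 = 0.826, a 17.4% reduction. With RR 0.85 as a ratio of annual rates and an overall rate of 4.2%, the higher arm is 4.2 × 2/1.85 = 4.54 and the lower 4.54 × 0.85 = 3.86, which is Table 6's 4.5/3.9. With RR 0.85 as a ratio of cumulative risks, the pair is about 4.56/3.84, which rounds to the text's 4.6/3.8. On that reading the higher-arm rates for Table 6's four overall rates are about 4.56, 4.78, 4.99 and 5.21, the list in the protocol text.

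**7. Scale of RR.** The test is Cox/log-rank. As a hazard ratio of 0.85, 1322 events give ½ × 36.36 × 0.1625 − 1.96 = 0.99, so 84.0%. The counts 1383, 1439 and 1503 give 85.6%, 86.9% and 88.3%, and 1246 gives 81.8%. As a ratio of cumulative risks, 1322 events mean p₁ = 1322/(7,500 × 1.85) = 0.0953 and p₂ = 0.0810. The two-proportion power is then 87.0%, and 1246 events give 84.8%. The stated figures are 88% and 85%.

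**The case against.** Four objections deserve weight.

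**The 44-month origin.** A reader might infer that Table 7 is shown to be a mislabelled 44-month table. It is not. The accrual curve is unpublished, and the close fit needs slow-start accrual and rates read as annual probabilities. Nine matching cells are also nearly one match, because at low rates every count is close to 15,000 × mean rate × one exposure constant. This stands: 44 months is the likeliest explanation, but an inference. The conflict with Table 6 and with the SAP's 642 events does not depend on it.

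**The rate pair.** It is tempting to say that 4.6%/3.8% is an error for 4.5%/3.9%. The documents do not support that. One-decimal rounding lets 3.8/4.6 cover 0.806 to 0.846, which includes the hazard ratio of about 0.84 implied by a cumulative-risk reading. That reading best recovers the printed powers, so Table 6's row and the SAP's 4.5% could be the mismatched entries. Only the disagreement is established.

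**Effectiveness power.** A reader might infer that the stated 88% is overstated. That holds only if RR means a hazard ratio. On the cumulative-risk reading it stands to within about one point, and on either reading it exceeds 80%.

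**Consequence.** The safety figures err on the low side, the protocol bases the choice of 15,000 and 50 months on effectiveness, and the SAP describes enrollment as past. A new table cannot alter the design. This also stands and keeps the point minor, but the stated power of the primary safety endpoint still has to be right when the result is read.

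**Conclusion.** The point holds as a minor documentation error. Table 7 cannot share Table 6's stated enrollment, follow-up and loss on any one accrual pattern tried. SAP 7.6 gives more safety events at a shorter follow-up than Table 7 does at a longer one. The SAP's 642 and 1246 events also appear to rest on different accrual. The safety power of the 50-month design is therefore stated correctly nowhere. At 2.5% and a 20% reduction it is about 85%, against 76% and 81% in print, so the chance of missing that effect is about 15% rather than 24% or 19%.

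These figures assume exponential event and loss times and accrual inferred from the documents' own event counts. They vary by about one point over the shapes and rate readings tried. The mismatch between the protocol text and Table 6 is certain; which entry is right is not. The unstated scale of RR moves effectiveness power at 1322 events between 84% and 87%. Nothing here shows an underpowered trial or a wrong sample size.

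**What to change.** 1. Recompute Table 7, its summary sentence and the SAP 7.6 safety paragraph at 50 months on the accrual pattern used for Table 6, and state that pattern in both documents. Expect about 93% or more for a 25% reduction at every rate and, for a 20% reduction, about 76–77%, 85% and 90–91% at 2%, 2.5% and 3%. If Table 7 was meant for 44 months, relabel it and add the 50-month figures.
2. Return to the PASS output and reconcile the protocol's rate list, its 4.6%/3.8% pair, Table 6 and SAP 7.6, without presuming which is right. Remove the word overall from the SAP's higher-risk-arm rate, since Table 6's overall rate in that scenario is 4.2%.
3. State the scale of RR. If it is a hazard ratio, restate Table 6's RR 0.85 powers as 84/86/87/88% and the SAP figures as 84% (1322 events) and 82% (1246 events). If it is a ratio of cumulative risks, say so and give the implied hazard ratio, about 0.84.

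The cost is one rerun and text edits. Stated safety power rises. Effectiveness power is unchanged, or about 3 to 4 points lower in the RR 0.85 rows if RR is a hazard ratio. Sample size, test and alpha stay as they are.

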These data will be analyzed, and the trial statistician will provide them to the DSMB regularly. The DSMB will review the data every 6 months and recommend any necessary changes to the conduct of the trial. Given that aspirin has been used for more than a century and most SAEs have been reported in conjunction with its use, the rate of unsuspected SAEs that the sites will/can submit through MedWatch to the FDA is expected to be very low.

III.F. Summary of Statistical Methods

III.F.1. Baseline Demographic, Clinical, Functional, and Procedural Characteristics

Descriptive summaries of baseline demographic and clinical variables will be generated for each randomized treatment arm of the study. Continuous baseline variables will be presented as medians with 25th and 75th percentiles, and discrete variables will be summarized using frequencies and percentages.

III.F.2. Populations for Analysis

The ITT population will consist of all patients randomized to a treatment group in the study regardless of their compliance with the study medication. For all analyzed using the ITT population, participants will be analyzed as randomized.

The per-protocol population is a subset of the ITT population, excluding participants who complied with the randomized treatment for less than 50% of the follow-up or had major protocol deviations expected to affect the primary effectiveness or safety endpoint.

III.F.3. Primary Effectiveness Comparison

The primary endpoint of this study will be survival free from the first event of a composite of all-cause death, hospitalization for nonfatal MI, or hospitalization for nonfatal stroke. Specifications for the identification of these endpoints are provided in **Section III.A.5.** The primary effectiveness analysis will be performed by the ITT principle based on randomized treatment assignment. Event-free survival rates will be compared using Cox proportional-hazards models. ⁹⁶ In the absence of any other covariates, this is the same as the log-rank test. ⁹⁰ The test will be 2-tailed and will be performed at an overall alpha of 0.05.

III.F.4. Primary Safety Comparison

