The DSMB may recommend stopping the trial for any safety-related concern at any time. Particular attention will be paid to all-cause mortality. For effectiveness, the trial will compare doses of aspirin that have been proven effective in previous trials, and thus it is unlikely that any dramatic differences will appear early. However, the DSMB will monitor these differences about every 6 months over the 3.5 years of the trial. Thus, we anticipate 6 interim analyses and 1 final analysis. Because there are multiple tests, each test must be made at an adjusted alpha level using group sequential-testing methods. To minimize the chance of stopping early due to a spurious result, the endpoints will be tested at the planned analyses using a specific method known as the Haybittle-Peto rule. 101 This rule tests the

endpoints at the 0.001 level (z = 3.29, two-sided) at each interim review and then makes the final test at the 0.0499 level (z = 1.9605). Thus, there is only minimal penalty for interim analyses.

The decision-making structure and process for the DSMB will be described in a separate DSMB charter.

III.G.6. Data Auditing Conventions

Data will be collected via the study patient portal (Sections III.A.3.c and III.A.3.h).

IV. Human Subjects

IV.A. Protection of Human Subjects

IV.A.1. Sources of Data

Data obtained from the study participant web portal, from the CDM, from Centers for Medicare Services, and from HealthCore/Anthem Research Network, an HPRN, will be transferred to the DCRI along with unique participant identifiers. Details for the process and authorization for Medicare and health plan data linkages are contained in a separate Linkage Plan document. Data contained within the CDM will be obtained from each of the recruiting sites and the HPRN and will be transferred to the DCRI. The control of access to databases at DCRI will be managed centrally by the DCRI through user passwords linked to appropriate access privileges. This protects data from unauthorized view and modifications as well as inadvertent loss or damage. Within the secondary SAS databases, UNIX group access control will be used for maintaining similar security. The Sun workstation login will be secured by extensive user password facilities under UNIX.

IV.A.2. Potential Risks

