7.3 Primary Effectiveness Comparison

The primary endpoint of this study will be event-free survival from the first event of a composite of all-cause death, hospitalization for nonfatal myocardial infarction, or hospitalization for nonfatal stroke. The primary effectiveness analysis will be performed in the ITT population based on randomized treatment assignment. Event-free survival rates will be compared using Cox proportional-hazards models, equivalent to the log-rank test, using censoring rules described in Section 7.5. The test will be two-tailed and will be performed at an overall α of 0.05. The proportional hazards assumption will be checked for the randomized treatment assignment using weighted Schoenfeld residuals. If there is evidence of non-proportionality, a cautious interpretation of the Cox model hazard ratio will be encouraged, and non-parametric event rate estimates will be emphasized (see below).

In addition to Cox regression, cumulative endpoint event rates will be estimated as a function of follow-up time in each treatment group using Kalbfleisch & Prentice's nonparametric estimator of the cumulative incidence function (CIF). The Kalbfleisch & Prentice CIF estimator is equivalent to the Kaplan-Meier estimator when applied to endpoints that are not subject to competing risks. Cumulative endpoint event rates and differences in cumulative endpoint event rates will be

estimated and presented with 95% confidence intervals. These non-parametric analyses are important for descriptive purposes and will be a focus of interpretation if the event rate curves cross. They may also be used to construct summary measures of treatment effect which are interpretable when the proportional hazards assumption is violated.

Sensitivity analyses for potential misclassification and under-reporting of endpoints and for nonadherence to randomized aspirin dose are described in Section 7.10. An additional sensitivity analysis will be performed to take clustering of patients within sites into account, using the robust sandwich covariance estimator.

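### The protocol's final test level of 0.0499 does not hold overall alpha at 0.05 after six interim tests at 0.001, and the SAP gives no nominal final level

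*Protocol*

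**What the plan says.** Protocol III.F.3 sets the error rate for the primary effectiveness test: "The test will be 2-tailed and will be performed at an overall alpha of 0.05". III.F.4 sets the same rate for the bleeding comparison.

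Protocol III.G.5 describes the monitoring. On timing it says: "However, the DSMB will monitor these differences about every 6 months over the 3.5 years of the trial". On the count: "Thus, we anticipate 6 interim analyses and 1 final analysis". On the standard to be met: "each test must be made at an adjusted alpha level using group sequential-testing methods". It names the Haybittle-Peto rule, tests at two-sided 0.001 (z = 3.29) at each interim review, and "then makes the final test at the 0.0499 level (z = 1.9605"). It describes the cost of the interim tests as minimal. It gives no information fractions and no calculation behind 0.0499.

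III.F.5 has since lengthened the trial: "Furthermore, maximum follow-up will be increased to a maximum of 50 months".

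SAP 7.3 says: "The test will be two-tailed and will be performed at an overall α of 0.05". SAP 7.4 says the same for bleeding. Neither section mentions interim tests, the Haybittle-Peto rule, 0.001 or 0.0499. The SAP synopsis says that many details are also in the protocol, "with some differences in proposed statistical methodology".

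**The concern.** The protocol does not leave the final test unadjusted. It commits to a group-sequential adjustment and prints a level and a z-value to four decimals. That number should therefore deliver the promised 0.05, but it is too close to 0.05 to pay for six earlier tests at 0.001 spread over the whole trial.

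What is at stake is narrow. With a final p-value just under 0.0499, the protocol would declare significance without the error control that it promises. The SAP does not settle the matter, because it never states the nominal level for the final test. A dispute about the threshold is hard to resolve fairly once the results by arm are known.

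**Working it through.** **Inputs from the documents**
- Overall two-sided alpha 0.05 (Protocol III.F.3 and III.F.4; SAP 7.3 and 7.4).
- Six interim tests at 0.001 and a final test at z = 1.9605, about every 6 months over 3.5 years (Protocol III.G.5).
- Accrual 38 months, maximum follow-up 50 months, loss 5% per year (III.F.5).
- Overall event rate 4.2% per year, with 1322 events at a relative risk of 0.85 (Table 6).

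**Assumptions**
- Look timing, because no information fractions are given.
- Uniform accrual and exponential event and loss times for the calendar schedules.
- Any interim crossing, in either direction, counts as a rejection. This is the usual convention.

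**The stated figures.** z = 1.9605 corresponds to two-sided p = 0.04994 and z = 3.29 to p = 0.00100, so each level matches its z-value. Subtraction does not explain 0.0499: 0.05 − 0.001 = 0.049, and 0.05 − 6 × 0.001 = 0.044.

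**Overall error.** Under the null hypothesis the statistics Z₁,…,Z_K, with Z_K the final one, are jointly normal with correlation √(t_j/t_k) between looks j < k, where t is the information fraction. Then

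overall error = P(|Z_k| ≥ 3.2905 at any interim) + P(no interim crossing and |Z_K| ≥ 1.9605),

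obtained by recursive numerical integration. For the calendar schedules, t is the expected number of events at the look divided by the number at the final analysis. A participant followed for time s contributes λ/(λ+η) × (1 − e^(−(λ+η)s)), with λ = 0.042/12 and η = 0.05/12 per month, averaged over entry times.

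| Assumed looks | Information fractions at interims | Overall error | Final z (level) that holds 0.05 |
|---|---|---|---|
| Six, equally spaced | 1/7 to 6/7 | 0.00420 + 0.04730 = 0.0515 | 1.9736 (0.0484) |
| Months 6–36, final at 42 | 0.023, 0.089, 0.197, 0.345, 0.531, 0.753 | 0.00500 + 0.04774 = 0.0527 | 1.9848 (0.0472) |
| Months 6–36, final at 50 | 0.017, 0.068, 0.150, 0.262, 0.403, 0.572 | 0.00500 + 0.04814 = 0.0531 | 1.9886 (0.0467) |
| Months 6–48, final at 50 (eight looks) | as above, plus 0.760, 0.941 | 0.00611 + 0.04704 = 0.05315 | 1.9887 (0.0467) |

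A simulation of 4 million trials with equal spacing gave 0.0514 (Monte Carlo standard error 0.0001).

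**Sensitivity**
- Event rates from 3.8% to 5.0% per year move the calendar results by less than 0.0001.
- Modelling the slow start described in III.F.5 as a 14-month linear ramp gives about 0.0533 (final at 42) and 0.0537 (final at 50, eight looks). These are approximate, because the earliest looks hold very few events.
- Dropping the two earliest looks gives 0.0511 (final at 42) and 0.0515 (final at 50).
- Six looks between 50% and 95% of the information give 0.0503.
- The total falls to 0.0499 if all six looks lie between 90% and 99% of the information.
- With a single interim, z = 1.9605 gives exactly 0.05 when that look is at about 66% of the information. A single look at 50% gives 0.0502.

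**Power.** By the Schoenfeld formula, power = Φ(½√1322 × ln(1/0.85) − z) = Φ(2.9545 − z). This gives 0.840 at level 0.0499, 0.837 at 0.0484, 0.834 at 0.0472 and 0.833 at 0.0467.

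**The case against.** The strongest case on the other side accepts the arithmetic and disputes its weight.

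- **Size.** The excess is a fraction of a percentage point, and the protocol claims only a minimal penalty. This is true, and it limits the importance of the point. It does not make 0.0499 the level that delivers 0.05.
- **Timing.** The totals near 0.053 depend on formal tests at about 2% and 7% to 9% of the information. The first would be about 22 events (0.017 × 1322) for a month-50 final, and such tests may not have been done. This stands as a caution about the upper end. Without those looks the total is still 0.0511 to 0.0515, and the schedule as written does call for six looks about every 6 months. Only looks bunched near the end bring the total to 0.05 or below, which contradicts that schedule.
- **Crossings may not be claims.** The DSMB may recommend stopping but need not, and its charter is a separate document that was not available. If an interim crossing could never lead to a claim of a difference, the final test alone would be at 0.0499. But then no adjusted level would be needed, and III.G.5 says that one is.
- **SAP silence is not contradiction.** An overall 0.05 is compatible with a lower nominal final level, so 0.0499 is the only final level on record. That is fair. The SAP still leaves the operative threshold unstated while announcing methodological differences from the protocol.
- **Number of looks.** Moving from six to eight changes the total only from 0.05314 to 0.05315. The 3.5-year wording is out of date but has no numerical consequence.

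**Conclusion.** The concern holds. On the schedule that the protocol describes, a final level of 0.0499 after six interim tests at 0.001 gives an overall error of 0.0515 to about 0.053, which is 0.15 to 0.3 percentage points above the promised 0.05 (up to 0.37 with a slow enrolment start). The range rests on assumed look timing and on counting any interim crossing as a rejection. Fewer or later looks reduce the excess, but it disappears only with timing that does not fit reviews about every 6 months.

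The practical effect is small. It touches only a final p-value between roughly 0.047 and 0.0499. It should still be corrected, because a stated decision threshold ought to deliver its stated error rate and the correction is cheap. The outdated look count and the unclear scope for bleeding (III.G.5 refers only to the endpoints in general) are clarifications and add nothing to the numerical finding.

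**What to change.** In Protocol III.G.5 and SAP 7.3, replace the fixed 0.0499 (z = 1.9605) with a final two-sided level computed so that the overall error is 0.05, given the interim looks actually done at 0.001 and their information fractions. List those looks and fractions in the SAP. Do not substitute another fixed number such as 0.0484, which is right only for six equally spaced looks. Do this before the final comparison by arm.

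In the same edit:
- State whether the rule also covers the bleeding endpoint and, if it does, say so in SAP 7.4.
- Report the confidence level that matches the final test: about 95.2% (1 − 0.0484) to 95.3% (1 − 0.0467) on the schedules above.
- Bring the 3.5-year look count into line with the 50-month maximum follow-up.

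The cost is one SAP paragraph and one protocol line. The threshold becomes stricter by 0.0015 (0.0499 − 0.0484) to about 0.003 (0.0499 − 0.0467 = 0.0032). Power at 1322 events and a hazard ratio of 0.85 falls from 0.840 to no lower than 0.833.
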